3.7.1.2.2. Pediatric Daytime Sleepiness Scale scores (PDSS)

This is a simple instrument constituted by 8 items ("How often do you fall asleep or get drowsy during class periods", "How often do you get sleepy or drowsy while doing your homework", "Are you usually alert most of the day", "How often are you ever tired and grumpy during the day", "How often do you have trouble getting out of bed in the morning", "How often do you fall back to sleep after being awakened in the morning", "How often do you need someone to

awaken you in the morning", "How often do you think that you need more sleep") each of them scored in 5 categories (Appendix 3).

Each of the eight questions is rated from 0 = never, 1 = seldom, 2 = sometimes, 3 = often, frequently to 4 = very often, always. The total score ranges between 0 and 32 with higher scores representing greater sleepiness. A score greater than 13 is considered as abnormal sleepiness.

PDSS will be evaluated at each study visit and reviewed by the investigator. PDSS should be administrated to the patient at approximately the same time of the visit day and with same delay after the investigational treatment intake in order to standardize the possible impact of the treatment on the evaluation.

The patient should be helped in the comprehension of the questionnaire until he fully understands the eight questions of the score. It will be reminded to the patient that the PDSS measures the subjective sleepiness with regard to the immediate past week.

It occurs frequently that some questions on specific situations are not encountered by the patient in his/her daily life. It is advised to give the patient equivalence to a similar situation in order to have a complete questionnaire filled. The sum of the rated questions will be made by the investigator and reported in the CRF.

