3.4.1. Inclusion criteria

- 1) Male and female children from 6 to less than 18 years of age (at V8) suffering from narcolepsy with or without cataplexy meeting the International Classification of Sleep Disorders (ICSD-3) criteria (Narcolepsy type 1 and 2). Diagnosis confirmed with polysomnography and Multiple Sleep Latency Test for patients without cataplexy (if these examinations were not performed within the last 12 months)
- 2) PDSS score \geq 15 during baseline period (V1+V2) / 2.

- 3) Patients should be free of non-authorized medication, in particular psychostimulant treatments as from the screening visit (V0) onwards.
- 4) Parents and patients old enough to understand who have expressed a willingness to participate in the study, who have signed and dated the informed consent form prior to beginning protocol required procedures.
- 5) In the opinion of the investigator, the patient must have adequate support to comply with the entire study requirements as described in the protocol (e.g., transportation to and from trial site, self rating scales and diaries completion, drug compliance, scheduled visits, tests).
- 6) Female pubescent patients shall use a birth control method, judged efficient by the investigator, throughout the study and during the month following treatment discontinuation.
- 7) Patients should benefit from appropriate healthy insurance system (only applicable where mandatory e.g. in France).

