# 4.5.3.2 Secondary endpoints

# 4.5.3.2.1 Pediatric Daytime Sleepiness Scale scores (PDSS)

PDSS is a sum score with 8 items leading to a score range of 0-32. A score greater than 13 is considered as abnormal sleepiness.

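### Protocol 3.7.1.2.2 scores all eight PDSS items never = 0 to always = 4 with higher meaning sleepier, but one item asks about alertness and no reversal is stated

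*Protocol*

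**What the plan says.** Protocol 3.7.1.2.2 lists eight PDSS items. Seven ask about drowsiness, tiredness, difficulty waking or need for sleep. The other asks "Are you usually alert most of the day". One rating rule covers them all: "Each of the eight questions is rated from 0 = never", rising to often, "frequently to 4 = very often, always". The investigator adds the ratings and enters the sum in the CRF. On direction the section says: "The total score ranges between 0 and 32 with higher scores representing greater sleepiness". The abnormality cut-off follows: "A score greater than 13 is considered as abnormal sleepiness".

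The SAP (4.5.3.2.1) says "PDSS is a sum score with 8 items leading to a score range of 0-32" and repeats the cut-off. SAP 4.1.5.5 adds the responder rule, a fall of at least 3 points from baseline to final value. It has no PDSS item list, anchors or coding table.

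PDSS is used in three places:

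- Entry: protocol 3.4.1 requires a score of at least "15 during baseline period (V1+V2) / 2".
- Testing order: SAP 4.1.3.2 tests PDSS second, directly after UNS and ahead of UNS-CTP, WRC and MWT.
- Response: SAP 4.5.3.2.1 compares the PDSS responder rate between arms.

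**The concern.** The statements in protocol 3.7.1.2.2 cannot all hold. If the alertness item is rated never = 0 and always = 4 and then added in, a more alert child gets a higher total, while the section says a higher total means a sleepier child. This is a stated rule that misfires when followed, not merely a missing detail.

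If sites score as the text reads, improvement in alertness is subtracted from the PDSS benefit instead of added to it. The entry threshold then means different things for children with different alertness ratings, and some true responders are counted as non-responders. PDSS is also a gate: without a significant PDSS result, the fixed sequence does not go on to UNS-CTP, WRC and MWT. If some sites follow the prose and others follow a form with reversed points, the data would hold two codings under one name.

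**Working it through.** **Inputs.** Eight items, each 0 to 4; total 0–32, higher = sleepier; cut-off above 13 (all protocol 3.7.1.2.2). Entry mean at least 15 (protocol 3.4.1). Responder fall at least 3 (SAP 4.1.5.5).

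**The plan's own range.** 8 × 0 = 0 and 8 × 4 = 32, so 0–32 reproduces. It is the same whether or not the alertness item is reversed, so the range does not show which coding is meant.

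**Error per child.** Let S be the sum of the other seven items and a the alertness rating.

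- As written: S + a.
- Reversed: S + (4 − a).
- Difference: 2a − 4, which is −4, −2, 0, +2, +4 for a = 0, 1, 2, 3, 4.

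The sleepiest possible child (S = 28, a = 0) scores 28 as written and 32 reversed. The least sleepy (S = 0, a = 4) scores 4 as written and 0 reversed. The direction statement therefore fails under the written rule.

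**Entry criterion.** Points needed on the other seven items to reach 15, taking the same alertness rating at V1 and V2:

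| Alertness rating a | As written (15 − a) | Reversed (11 + a) |
|---|---|---|
| 0 | 15 | 11 |
| 1 | 14 | 12 |
| 2 | 13 | 13 |
| 3 | 12 | 14 |
| 4 | 11 | 15 |

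The written rule is stricter for children who are seldom or never alert and more lenient for those who are often or always alert.

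**Responder rule.** Let x be the fall on the seven items and k the gain in alertness. The recorded fall is x − k as written and x + k reversed, a gap of 2k. With x = 2 and k = 1, the recorded fall is 1 as written (non-responder) and 3 reversed (responder).

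**Illustration of dilution.** Assume all eight items improve by the same amount d.

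- Change as written: 7d − d = 6d. Change reversed: 8d. Ratio 6/8 = 0.75, so a true fall of 3/0.75 = 4 points is needed to record 3.
- Assume also equal item variances and a common inter-item correlation r, which the documents do not give. The SD ratio, written to reversed, is √[(7(1 + 6r) + 1 − 14r) / (8(1 + 7r))] = √[(8 + 28r)/(8 + 56r)]. The standardised-effect ratio is 0.75 divided by this.

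| Assumed r | SD ratio | Standardised-effect ratio | Loss of effect | Equivalent loss of sample (1 − ratio²) |
|---|---|---|---|---|
| 0.2 | √(13.6/19.2) = 0.842 | 0.891 | 11% | 21% |
| 0.3 | √(16.4/24.8) = 0.813 | 0.922 | 8% | 15% |
| 0.4 | √(19.2/30.4) = 0.795 | 0.944 | 6% | 11% |
| 0.5 | √(22/36) = 0.782 | 0.959 | 4% | 8% |

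**The case against.** The strongest point on the other side is that the instrument itself is not visible. The protocol refers to Appendix 3 for the five response categories, and that form may print reversed points for the alertness item. The CRF cited in the SAP introduction is not visible either. Nothing says that the prose overrides the form. A reader might infer that PDSS totals in this trial are wrong; the documents do not show that. This stands, and it limits the point to a contradiction in the text plus a check.

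A reader might also take both documents to prescribe the never-to-always rating. Only the protocol does. The SAP gives a sum and a range, and its fault is only that it does not resolve the contradiction.

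The intended direction can be argued to be clear, since the statement that higher means sleepier holds for all eight items only if the alertness item is reversed. That is a fair reading of intent, but the same paragraph gives sites an explicit rating rule that defeats it.

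The SAP codes every UNS item in 4.1.5.5 and no PDSS item. This is weak evidence of a PDSS problem: the UNS tables serve the subscore derivation, and the SAP gives no item coding for CASS or CDI either.

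Finally, the 75% and the 4–11% rest on equal improvement across items and an assumed correlation, and the error in the total runs both ways. That also stands. If alertness did not respond to treatment (k = 0), the raw change would not be diluted at all.

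**Conclusion.** The point holds as a self-contradiction in protocol 3.7.1.2.2 that the SAP does not correct. It should be resolved before database lock. It is not evidence that scores were mis-summed.

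If the written rule was applied, each total is off by 2a − 4, between −4 and +4 points, and each one-category gain in alertness costs 2 points of recorded improvement. Those figures need no assumption beyond the stated coding. The 75% figure, and the fall of about 4% to 11% in the standardised effect for r from 0.5 down to 0.2, are illustrations only.

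The parts exposed are the entry threshold, the responder rate and the PDSS step of the fixed sequence. A reader might infer that the later secondary tests will be lost. That would need both an actual scoring error and a PDSS test that fails because of it, and neither is shown. Any miscoding would apply under blinding to both arms, so it would mainly dilute the effect and would not inflate type I error. UNS is the primary endpoint, so its analysis and the 108-patient calculation do not depend on PDSS coding.

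**What to change.** 1. Amend protocol 3.7.1.2.2 and add to SAP 4.1.5.5 that the alertness item is scored as 4 minus the frequency rating, or, if the form prints it that way, that its points are already reversed. In either case, correct the sentence that applies one rating to all eight questions. A short item table like the UNS ones would do this.
2. Before database lock and blind to treatment, check that Appendix 3, the CRF and the investigators' sums all use this coding.
3. Recompute totals from item-level data or source forms wherever they do not. Recomputing every total is warranted only if the check shows that it is needed.

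The text change costs a sentence in the protocol and a small table in the SAP. The check is modest if items are in the database. If the CRF holds only the total, a wrong sum cannot be repaired at analysis without the source forms, so the cost is then retrieving those forms.

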3.7.1.2.3. Clinical Global Impressions of Change

The severities of EDS and of cataplexy will be measured at baseline period V1 and V2 by the Clinical Global Impression of Severity (CGI-S) in order to describe the population: a 6-grade scale ranging from "no sign of illness", "borderline ill", "slightly ill", "moderately ill", "markedly ill", "among the most extremely ill patients" (Appendix 5). This corresponds to the first version of the test. When the patient is on treatment, the test enables to assess the improvement.

At visits V6 and V7 (during double-blind phase) and all visits of open-label period, the patients' change in EDS and in cataplexy (for narcoleptic patients also experiencing cataplexy) compared to baseline will be rated by the same investigator using Clinical Global Impression of Change (CGI-C) to document the perceived change in patients' illness: a 7-grade scale ranging from "very much improved", "much improved", "minimally improved", "no change", "minimally worse," "much worse", "very much worse".

3.7.1.2.4. Test of Everyday Attention for Children (TEA-Ch)

The Test of Everyday Attention for Children (TEA-Ch) assesses the cognitive functions with a version intended for children and another one for adolescents. This cognitive test shall be performed at V1 and at V6 visits.

3.7.1.2.5. Maintenance of Wakefulness Test 30-minute version

The Maintenance of Wakefulness Test (MWT) is used in this study to assess an individual's ability to maintain awake while resisting the pressure to fall asleep.

Patients will be administrated four 30-minute MWT sessions at 2-hour intervals at inclusion visit (V2) and at endpoint visit (V7 or the last on-study visit), according to validated standard [Doghramji K et al, Electroencephalogr Clin Neurophysiol. 1997; 103:554-62]8.

Patients will be required to have sufficient nocturnal sleep (minimum 6 hours) and not drink alcohol during the night prior to this visit. The patient will be required to take their morning treatment and a light breakfast before 8.00 a.m. and arrive in the trial center around 9.00 a.m.; lunch immediately after the termination of the second session. They should refrain from drinking any stimulatory beverage such as coffee, tea or Coca-Cola this morning until the end of this visit.

The first session begins at 10.00 a.m. Patients are required to recline comfortably in a quiet, dimly lit bedroom at ambient temperature (as close to 22°C as possible). Patients are instructed to remain awake for as long as possible. Sleep onset is defined by either 3 consecutive 30-s epochs of stage 1 sleep or any single 30-s epoch of stage 2, 3, 4 or REM sleep.

Each session is terminated either at the first unequivocal onset of sleep defined as above or, if sleep onset is not achieved, after maximum in-bed duration of 30 minutes. Polysomnographic recordings are made to determine sleep onset, and mean sleep latency is calculated (maximum score 30 minutes).

3.7.1.2.6. Patient sleep diary

Patient sleep diary (Appendix 6) information from V1 (or from V0 when applicable) to V8 will be analyzed.

Patients (or assisted by their parents or legal representative or teacher) shall fill in the document on a daily basis throughout the double blind phase (13 weeks) and the 7-day prior to the next visit during the open-label period. During the first screening visit (V1 or from V0 when applicable), patients will be instructed on the daily use of diary by study investigators.

At each visit the patient should bring back his/her diary to the site for review by the investigator. The investigator should review these records with the patient.

In the active treatment group and in the placebo group, the score difference between the average number of cataplexy episodes (partial and total) per weeks between the 2 weeks of baseline and the 2 weeks of end study treatment period (V6, V7) and the differences in weekly frequency of cataplexy episodes between baseline and the 4 weeks of stable treatment period (V4 to V7).

In the open-label period, the difference between, the average number of cataplexy episodes

(partial and total) per weeks, the differences in weekly frequency of cataplexy episodes, between baseline and the 7-day prior all visits of the open-label period will be compared.

From the sleep diary, it will also be possible to check: Investigator should review the patients' and parents' estimate with them

- Hour of bedtime in the evening, wake-time in the morning.
- Number of diurnal involuntary sleep attacks and episodes of severe daytime sleepiness.
- Occurrence and number of cataplexy attacks (total or partial).
- Number of hallucinations and sleep paralysis.

3.7.1.2.7. Patient's Global Opinion on the effect of treatment

At V7 and all visits of open-label period, patients' global opinion will be reported by patient if able to express himself. If not, either their parents or their main teachers should evaluate the Global effect of the treatment by comparing the period prior to that visit with the patient's prestudy condition.

The following six-level scale will be used:

- Marked effect (complete or nearly complete remission of EDS)
- Moderate effect (partial remission of EDS)
- Minimal effect (slight decrease in EDS that does not substantially alter the status of the patient)
- No change
- Minimally worse (slight increase in EDS)
- Much worse (substantial increase in EDS)

3.7.1.3. Compliance

The compliance with study medication will be assessed by comparing the amount of medication remaining at each visit with the amount predicted to remain if the patient is compliant with the prescription.

3.7.2. Safety criteria

The safety criteria will include:

- Adverse and unexpected events, emergent or not, reported during the study course (frequency, severity, relationship to study drug, incidence and occurrence)
- Change of vital signs parameters (heart rate, blood pressure, body weight) from baseline values

• Physical examination: abnormalities in each system class and change from baseline

• ECG parameters: in particular, calculation of the QTcF value and comparison with the QTcF value of the ECG performed at baseline. If the QTcF is \geq 500 ms or Δ between the QTcF on treatment and the QTcF at baseline is \geq 60 ms, the treatment shall be discontinued and the corresponding ECG forwarded to Bioprojet.

- Laboratory abnormalities (e.g. AEs will be defined as laboratory test results that are outside the reference range as defined by the normal range for laboratory test and clinically signification).
- Occurrence of withdrawal symptoms (to be checked during the phone call at D59 \pm 1 and at V8 end-of-study visit (D63).

3.7.2.1. Cardiovascular safety: vital signs and ECG

Vital signs including blood pressure, heart rate and body weight will be checked at the each visit.

ECG will be performed at each visit from the screening visit (V1) to the end of the double blind-phase (V8) or at early withdrawal visit and all visits of the open-label period. The main ECG parameters including calculation of Fridericia's corrected QTc interval (QTcF = QT/ 3 \sqrt (60/HR)) and intra individual changes in these parameters will be reported and analyzed locally. If the QTcF value is \geq 500 ms, or if the change from baseline is \geq 60 ms, (observed on two consecutive occasions, i.e. after performing a recheck a few hours later) the treatment shall be discontinued and ECGs (baseline and abnormal ECG) shall be dispatched to Bioprojet.

All ECGs will be reviewed a posteriori by a central reviewer.

3.7.2.2. Physical examination

A full physical examination will be performed at screening period (V0 (when applicable) and V1) and at each visit from V2 to V8 (or at early withdrawal visit) and all visits of the open-label period. Any significant abnormality and change from baseline will be recorded in the CRF and in the source document and will be analyzed as safety parameters. Any significant changes will be reported in the AE pages of the CRF.

3.7.2.3. Adverse events and Treatment Emergent Adverse Events

The safety will be assessed by the occurrence of adverse events, spontaneously reported by the patient or discovered during investigator's interview at each visit.

All of them must be reported by the investigator in the special form placed at the end of the CRF, whatever the nature, the intensity, the severity and the supposed causality from the study

BIOPROJET Version 3.0
Protocol P11-06/ BF2.649 September 30th, 2020
EudraCT number: 2013-001506-29

compound.

For each adverse event, the investigator shall report the nature, the anteriority (emergent or not),

the date of apparition, the intensity, the severity and the action taken in regard to the study

treatment, and the concomitant therapies.

When the event ends or at the end of the study, the investigator must report the evolution from

the event and evaluate the relationship to the study compound.

The events will be categorized by System Organ Class and Preferred Terms (MedDRA) and

type, severity and relationship to the treatment.

All Adverse Events and unexpected events, emergent or not, reported during the study course

(frequency, severity, relationship to study drug, incidence and occurrence) will be analyzed.

Treatment Emergent Adverse Events (TEAE) defined as any event not present prior the

initiation of the study treatment or any event already present that worsens in either intensity or

frequency following exposure to the study treatment, will be analyzed as the main safety

parameters.

3.7.2.4. Blood Laboratory tests, urinalysis, urinary drug testing

A full laboratory test should be performed at screening (V1), at the final double-blind treatment

phase evaluation visit (V7) and at early withdrawal visit and during the open-label period at

V10, V13 and all subsequent visits. Blood samples will be collected and all laboratory tests

will be performed according to the Good Laboratory Practice (OECD GLP Principles) by site-

dependent Laboratory. The results of laboratory tests will be interpreted by the investigator.

Laboratory abnormalities will be defined as laboratory test results that are outside the reference

range as defined by the normal range from the testing laboratory. Clinically significant

abnormal value at V1 will be determined by the investigator and will exclude patients from

study participation. The results of abnormal values of laboratory tests will be reported in the

CRF beside the normal range value given by the testing laboratory, the original document

containing all the tested values will be kept in the patient study file.

Blood laboratory test parameters and intra individual changes in these parameters will be

reported and analyzed in all patients.

- Hematology: Red Blood Cells, White Blood Cells (differential count, absolute value),

hemoglobin, haematocrit, Mean corpuscular volume (MCV), platelet count.

- Biochemistry: sodium, potassium, chloride, creatinine, alkaline phosphatases, urea,

alanineaminotransferase (ALAT), aspartate aminotransferase (ASAT), gamma glutamyl

BIOPROJET Version 3.0 Protocol P11-06/ BF2.649 September 30th, 2020

EudraCT number: 2013-001506-29

transpeptidase (GGT), total bilirubin, glucose, triglycerides, total cholesterol, quick time.

- Hormonology: βHCG (only for pubescent female).

- Urinalysis: semi-quantitative ("dipstick") analysis for pH, ketone bodies, proteins, glucose,

blood. If any of these parameters gives a positive result, a quantitative analysis will be

performed to characterize or count: crystals, casts, epithelial cells, white blood cells, red blood

cells and bacteria if required by the investigator.

- Urine drug testing: test of abuse of drugs will be performed on urine samples from 12 years.

Screened drugs are amphetamines, barbiturates, benzodiazepines, cannabinoids (THC) and

Opioids.

3.7.2.5. Childhood Depression Inventory

The Childhood Depression Inventory scale is a self-administrated 27-item questionnaire

commonly used in research to assess depression. The short version 2 of 12 items is used in the

study (Appendix 4). The patient is asked to pick out the statement in each of the 12 items which

best describes the way he feels right now at the moment of the assessment.

The range of scores for the scale are 0-4 = none or minimal; 4-7 = mild; 8-15 = moderate; ≥ 16

= severe depression.

The CDI questionnaire will be evaluated during double blind period at visits V1, V4, V6 and

V8 and all subsequent visits for the open-label period. Patients presenting severe depression

 $(CDI \ge 16)$ should be immediately withdrawn from the study for security.

